### 2.2.1 Subgroup of interest

Summary of the primary variable will also be presented by the below subgroups:

- ASAS-NSAID
  - Lower user groups (baseline score <75)
  - Higher user group (baseline score  $\geq$ 75)
- Gender
  - Male
  - Female

## 2.3 Patient disposition, demographics and other baseline characteristics

All data about disposition, patient demographics and baseline characteristics, including derived variables, will be summarized by treatment groups (secukinumab delayed tapering, secukinumab early tapering and placebo) and overall with summary descriptive statistics for all the patients in Randomized set. Continuous data will be summarized by n, mean, standard deviation, median, first and third quartiles, minimum and maximum. Categorical data will be presented by absolute frequency and percentages.

The number of the analysis populations will be described and the reasons for excluding a patient from any particular population will be provided with the number of protocol violators for each criterion. The difference between treatment groups with respect to protocol deviations and reasons for dropout will be examined by summarizing the protocol deviations by treatment groups and overall on the all patients.

### **2.3.1 Patient disposition**

Summary of disposition for screening phase and study completion phase will be presented separately.

For screening phase disposition, the number and percentage of patients screened, completed screening phase, screen failures along with the reasons for screen failures as captured in CRF and randomized for all screened patients.

For study completion phase disposition, the number and percentage of patients completed the study and discontinued from the study will be summarized by treatment groups and overall with reasons for discontinuation for all patients in Randomized set.

Listing for patients whether they completed or discontinued from the study at screening phase and study completion phase disposition will be provided separately with the date of discontinuation and primary reason for discontinuation. Listing for protocol deviations will be presented separately for all the patients in Full Analysis Set.

### **2.3.2 Patient demographic and other baseline characteristics**

The following demographic and baseline variables, if collected, will be summarized based on randomized set:

#### **Demographic variables:**

##### Continuous variables:

- Age (years)
- Height (cm)
- Weight (kg)
- BMI (kg/m^2) will be calculate as (body weight in kilograms) / (height in meters)
- Smoking usage (Pack years)

##### Categorical variables:

- Age categories (<65 years, >=65 and <75 years, 75 years and older)
- Gender (Male, Female)
- Race (Caucasian, Black, Asian, Other)
- Smoking status (Never, current, former)
- Source of patient referral
  - Physician's own practice
  - Physician referral
  - Print advertisement
  - Newsletter/educational material
  - Novartis internet site

- Non-Novartis internet site
- Clinical trial registry
- Other

**Baseline disease characteristics variables:**

Continuous variables:

- Duration of disease (months)
- Dose of methotrexate or other DMARD at randomization
- Patient's global assessment of disease activity
- Patient's assessment of back pain intensity
- BASMI
- BASDAI
- BASFI
- hsCRP
- ASDAS-CRP
- ESR (Erythrocyte Sedimentation Rate)
- ASDAS-ESR
- Number of prior biologic AS therapies
- ASAS Health Index
- SF-36 Physical Component Score
- SF-36 Mental Component Score

Categorical variables:

- TNF- alpha inhibitor status
  - Naïve
  - Inadequate responder
- History of Extra-Axial Involvement
  - Uveitis
  - Psooriasis
  - Inflammatory bowel disease
  - Dactylitis
  - Enthesitis
  - Peripheral arthritis

- HLA-B27 status
  - Positive
  - Negative
- hsCRP category
  - hsCRP-level  $\leq$  5 mg/L
  - hsCRP-level  $>$  5 mg/L
- ASDAS-CRP disease state
  - Inactive disease (ASDAS  $<$  1.3)
  - Low disease activity (ASDAS  $\geq$  1.3 and ASDAS  $<$  2.1)
  - High disease activity (ASDAS  $\geq$  2.1 and ASDAS  $\leq$  3.5)
  - Very high disease activity (ASDAS  $>$  3.5)
- NSAIDs or selective COX-2-inhibitors usage
- Corticosteroids (prednisone or equivalent) usage
  - $\leq$  7.5 mg/day
  - $>$  7.5 mg/day
- PPD test
  - Negative
  - Positive
- SF-36
  - Physical Component Score
  - Mental Component Score
- Environmental factors related to ASAS HI

### **Medical history**

Any significant prior or active medical condition as captured in CRF at the time of signing informed consent will be coded using the MedDRA dictionary. These medical conditions will be summarized by primary system organ class and preferred term.

Summaries for cardiovascular medical history and ankylosing spondylitis medical history will be provided as well, if collected.

Smoking history will be summarized by treatment group.

Unless otherwise specified, analyses will be based on the randomized set.

## 2.4 Treatments (study treatment, rescue medication, concomitant therapies, compliance)

### 2.4.1 Study treatment / compliance

The summaries by treatment will be performed by the randomized treatment or treatment sequence.

- Randomized treatment:
  - AIN457 150mg (delayed tapering)
  - AIN457 150mg (early tapering)
  - Placebo
- Treatment sequence:
  - AIN457 150mg (delayed tapering)
  - AIN457 150mg (early tapering)
  - Placebo-AIN457 150mg

The analysis of study treatment data will be based on the safety set.

#### **Duration of exposure**

Duration of exposure will be defined as the time from first dose of study treatment to the time of end of treatment period. For patients who discontinue, this will be the patient's last visit in the treatment period.

The exposure to investigational drug (number of doses) and duration of exposure to study treatment will be summarized by treatment group and overall.

In addition, the number and percentage of patients with cumulative exposure levels (e.g. any exposure,  $\geq 1$  week,  $\geq 2$  weeks,  $\geq 3$  weeks,  $\geq 4$  weeks,  $\geq 5$  weeks,  $\geq 6$  weeks,  $\geq 7$  weeks,  $\geq 8$  weeks,  $\geq 12$  weeks,  $\geq 16$  weeks,  $\geq 17$  weeks,  $\geq 18$  weeks,  $\geq 19$  weeks,  $\geq 20$  weeks) will be presented.

#### **Compliance**

Compliance will be calculated based on documented study treatment administration details and displayed by treatment group and overall. Total actual dose will be compared with the total dose patients should take as per protocol and derived compliance will be summarized.

Total actual dose will be derived as

Total actual dose = Actual amount of dose of Secukinumab 150 mg upto week 20  $\times$  Frequency of dose upto week 20.

The treatment compliance will be calculated by Statistical Programming team as

Treatment compliance (%) =  $\frac{\text{the actual number of injections received by a patient}}{\text{the scheduled number of injections}} \times 100$ .

Compliance is expected to be 100%, unless temporary interruption is needed for safety reasons. Compliance will also be assessed by a Novartis monitor using information provided by the authorized site personnel.

### **Drug interruptions**

The number and percentage of patients with permanent study drug interruptions and the reasons that led to the interruption will be summarized by treatment group and overall on the Safety set.

#### **2.4.2 Prior, concomitant and post therapies**

Prior and concomitant medications will be summarized in separate tables by treatment group. Prior medications are defined as treatments taken and stopped prior to first dose of study treatment. Any medication given at least once between the day of first dose of randomized study treatment and the date of the last study visit will be a concomitant medication, including those which were started pre-baseline and continued into the period where study treatment is administered.

Medications will be presented in alphabetical order, by Anatomical Therapeutic Classification (ATC) codes and grouped by anatomical main group. Tables will show the overall number and percentage of subjects receiving at least one treatment of a particular ATC code and at least one treatment in a particular anatomical main group.

Significant prior and concomitant non-drug therapies and procedures will be summarized by primary system organ class and MedDRA preferred term.

The number and percentage of subjects receiving prior and concomitant ankylosing spondylitis therapy will be presented by randomized treatment group as well as the reasons for stopping their therapies (primary lack of efficacy, secondary lack of efficacy, lack of tolerability, other) and the total duration of exposure to ankylosing spondylitis therapies previously.

Prior or concomitant medication will be identified by comparing recorded or imputed start and end dates of medication taken to the reference start date.

Safety set will be used for the above analysis.

## **2.5 Analysis of the primary objective**

The primary objective is to demonstrate that the efficacy of Secukinumab 150 mg s.c. (with NSAID tapering) is superior to placebo based on the proportion of patients achieving an ASAS20 response at week 12.

To show superiority, both Secukinumab treatment arms will be pooled and compared against placebo.

### **Primary variable**

ASAS20 response is defined as an improvement of  $\geq 20\%$  and  $\geq 1$  unit on a scale of 10 from baseline in at least 3 of the 4 main domains and no worsening of  $\geq 20\%$  and  $\geq 1$  unit on a scale of 10 in the remaining domain.

### 2.5.1 Estimand of primary variable

Proportion of patients fulfilling ASAS20 criteria in the pooled Secukinumab groups and Placebo regimen at Week 12. The analysis of the primary endpoint will be based on the FAS population. The analysis of the primary variable will be based on the following estimand:

- Population: patients in full analysis set
- Variable of interest: proportion of patients achieving treatment response as defined by the ASAS20 criteria at Week 12.
- Intervention effect: effect between a secukinumab pooled groups vs. placebo regardless of adherence to randomized treatment.
- Summary measure: Odds ratio (OR) of ASAS20 response for secukinumab pooled groups and placebo

### 2.5.2 Statistical hypothesis, model, and method of analysis of primary estimand

The statistical hypothesis for ASAS20 being tested is

$$H_0 : p_1 = p_0$$

v/s

$$H_1 : p_1 \neq p_0$$

where  $p_0$  denotes the proportion of ASAS20 responders in the placebo and  $p_1$  denotes the proportion of ASAS20 responders in the pooled Secukinumab groups at week 12.

Secukinumab groups will be pooled using their measurements at week 12.

The primary analysis will be performed using logistic regression with treatment, TNF- $\alpha$  status (previously exposed / never exposed), and CRP status (above central lab ULN / equal or below central lab ULN) as factors. The two Secukinumab groups will be pooled using a linear contrast.

Odds ratios and 95% CI will be presented comparing the Secukinumab (pooled) groups to placebo.

### 2.5.3 Handling of missing values/censoring/discontinuations

Missing data for ASAS20 response for data up to Week 20 will be handled as follows:

Non-responder imputation:

1. Patients who drop out of the trial for any reason will be considered non-responders from the time they drop out through Week 20.
2. Patients who do not have the required data to compute ASAS20 response at baseline and at the specific time point will be classified as non-responders.

Patients who were unblinded prior to the scheduled timepoint will be considered non-responders from the time of unblinding up to Week 16. The primary analysis will use the non-responder imputation.

Additionally, under the assumption of missing at random, multiple imputation by treatment may be performed for baseline weight as well as for all baseline and post-baseline efficacy variables of interest during the trial.

#### **2.5.4 Supportive analyses**

Sensitivity analyses and supportive analyses will be conducted in order to provide evidence that the results seen from the primary analysis are robust. These analyses will center on the deviations in model assumptions, and the treatment of missing data.

In addition, further logistic regression models may be conducted which explore the impact of other baseline or disease characteristics on response.

In case of a substantial number of missing values, their impact on the analysis results may be assessed as well by repeating the logistic regression model using ways to handle missing data. These may include, but are not limited to:

- a) Tipping point analysis
- b) Observed data analysis

These analyses will not be included in the CSR.

#### **2.6 Analysis of the key secondary objective**

Not applicable.

#### **2.7 Analysis of secondary efficacy objective(s)**

Refer to [Table 1.2-1](#) of Section 1 for the list of secondary objectives.

##### **2.7.1 Secondary endpoints**

The secondary efficacy variables are listed below. Secondary efficacy variables will be analyzed using the FAS population.

- ASAS20 response at Week 12/16.
- ASAS-NSAID response at Week 12.
- Change from baseline in BASDAI at Week 12/16.
- Change from baseline in SF36 physical component score at Week 12/16.
- Change from baseline in ASAS-NSAID score at Week 12 for Secukinumab (delayed tapering) vs. change from baseline in ASAS-NSAID score at Week 16 for Secukinumab (early tapering)
- Change from baseline in BASDAI at Week 12 for Secukinumab (delayed tapering) vs change from baseline in BASDAI at Week 16 for Secukinumab (early tapering).
- Change from baseline in BASDAI question 2
- ASAS20 response at Week 4 for Secukinumab (delayed tapering) vs. ASAS20 response at Week 20 for placebo group

Please refer to the main definition section.

## 2.7.2 Statistical hypothesis, model, and method of analysis

### Testing strategy

The following hypotheses will be included in the testing strategy, and type-I-errors will be set such that a family-wise type-I-error of 5% is kept:

#### Primary objectives:

[figure not shown]
- H1: Secukinumab 150 mg s.c. (pooled secukinumab groups) is not different to placebo regimen with respect to signs and symptoms (ASAS20 response) at Week 12.

#### Secondary objectives:

- H2: Secukinumab 150 mg s.c. (pooled Secukinumab groups) is not different to placebo regimen with respect to change from baseline in ASAS-NSAID score at Week 12
- H3: Secukinumab 150 mg s.c. (pooled Secukinumab groups) is not different to placebo regimen with respect to change from baseline in total BASDAI score at Week 12
- H4: Secukinumab 150 mg s.c. (delayed tapering) is not different to placebo regimen with respect to signs and symptoms (ASAS20 response) at Week 12
- H5: Secukinumab 150 mg s.c. (early tapering) is not different to placebo regimen with respect to signs and symptoms (ASAS20 response) at Week 12
- H6: Secukinumab 150 mg s.c. (early tapering) is not different to placebo regimen with respect to signs and symptoms (ASAS20 response) at Week 16.
- H7: Secukinumab 150 mg s.c. (delayed tapering) is not different to placebo regimen with respect to change from baseline in ASAS-NSAID score at Week 12.
- H8: Secukinumab 150 mg s.c. (early tapering) is not different to placebo regimen with respect to change from baseline in ASAS-NSAID score at Week 12.
- H9: Secukinumab 150 mg s.c. (delayed tapering) is not different to placebo regimen with respect to change from baseline in total BASDAI score at Week 12.
- H10: Secukinumab 150 mg s.c. (early tapering) is not different to placebo regimen with respect to change from baseline in total BASDAI score at Week 12
- H11: Secukinumab 150 mg s.c. (early tapering) is not different to placebo regimen with respect to change from baseline in total BASDAI score at Week 16.

These hypotheses will in principal be tested hierarchically in ascending order. However, since some hypotheses for individual group comparisons are already contained in the higher-ranked, pooled comparisons for the same endpoint (i.e. H4 and H5 are contained in H1, H7 and H8 are contained in H2 and H9 and H10 are contained in H3) these individual hypothesis can be tested simultaneously. The justification is that as soon as the pooled hypothesis has been rejected (e.g. H1), at least one of the two contained individual hypotheses (e.g. H4 and H5) must be false and there is only a potential for at most one type-I-error. Therefore H4 and H5 can be tested simultaneously once all higher-ranked hypotheses have been rejected. The same argument applies to H7 and H8 and to H9 and H10.

The following chart displays the testing strategy graphically:

First the hypotheses (H1) for the primary objective (ASAS20 for Secukinumab pooled at week 12) versus placebo will be tested. If this hypothesis can be rejected at level  $\alpha$ , H2 will be tested and so on until H4. H4 and H5 will be tested simultaneously. If both can be rejected, H6 will be tested and so on. As soon as a hypothesis fails to be rejected at level  $\alpha$ , all tests of the following hypotheses (except the paired hypothesis in the same knot) will be regarded as exploratory only and will not provide any confirmatory evidence, irrespective of their nominal p-values. Of note, in the description above, rejection of a hypothesis refers to rejection of the two-sided hypothesis; however the level of a rejected hypothesis is only passed on according to the procedure for the test of another hypothesis if the treatment effect is in favor of the Secukinumab

regimen. The family-wise error will be set to  $\alpha=5\%$  and it will be controlled with the proposed semi-hierarchical testing strategy.

## **Analysis of secondary efficacy variables**

### **ASAS20 at week 12**

Response at Week 12 to ASAS20 for Secukinumab (delayed-tapering) versus placebo will be evaluated using a logistic regression model with treatment as a factor and baseline weight as a covariate.

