The occurrence of relevant protocol deviations will be determined. After these actions have been completed and the database has been declared to be complete and accurate, it will be locked and the treatment codes will be unblinded and made available for data analysis. Any changes to the database after that time can only be made after written agreement by Trial Statistician and Statistical Reporting and the Clinical Trial Leader.

8.4 **Data Monitoring Committee**

Not required.

8.5 **Adjudication Committee**

Not required.

9 Data analysis

Summary statistics for continuous variables will generally include the number of subjects (N), minimum, lower quartile, mean, median, upper quartile, and maximum. For categorical or binary variables, the number and percent of subjects in each category will be presented. P-values presented will be two-sided unless otherwise specified.

Inferential efficacy comparisons with placebo will generally focus on the first 12-weeks of treatment.

Data analyses will be presented by treatment regimen. Efficacy and safety data for the placebocontrolled period (or the entire treatment period as appropriate) will be presented by the following 3 treatment groups. These treatment groups represent the regimens subjects will be eligible to be randomized to.

Secukinumab ("delayed tapering") regimen: Secukinumab 150 mg s.c. at Week 0, 1, 2, 3, 4, 8, 12, 16 and 20; Placebo injections at Week 5, 6 and 7 and 17, 18. 19.

Secukinumab ("early tapering") regimen: Placebo at Weeks 0, 1, 2, 3 followed by Secukinumab 150 mg s.c. at Week 4, 5, 6, 7, 8, 12, 16 and 20 with additional Placebo injections at week 17, 18. 19.

Placebo regimen: Placebo at Weeks 0, 1, 2, 3, 4, 5, 6, 7, 8 and 12. From Week 16, patients will be switched to receive Secukinumab 150 mg s.c. at Week 16, 17, 18, 19, and 20.

9.1 **Analysis sets**

Randomized set: The randomized set will be defined as all subjects who were randomized.

Full analysis set (FAS): The FAS will be comprised of all subjects from the randomized set to whom study treatment has been assigned. Following the intent-to-treat principle, subjects will be evaluated according to the treatment assigned to at randomization, and in the actual stratum if stratified randomization is used.

Safety set: The safety set includes all subjects who took at least one dose of study treatment during the treatment period. Subjects will be evaluated according to treatment received.

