Response at Week 16 to ASAS20 for Secukinumab (early-tapering) versus placebo will be evaluated using a logistic regression model with treatment as a factor and baseline weight as a covariate.

ASAS-NSAID at Week 12

Between-treatment differences in the change in ASAS-NSAID relative to baseline will be evaluated using a mixed-effect model repeated measures (MMRM). Treatment group and analysis visit as factors, baseline ASAS-NSAID and weight as continuous covariates. Treatment by analysis visit and baseline ASAS-NSAID by analysis visit will be included as interaction terms in the model. An unstructured covariance structure will be assumed for the model. The significance of the Secukinumab pooled treatment effect will be determined from a linear contrast comparing the (mean of the) two Secukinumab regimens to placebo. The significance of the two individual Secukinumab treatment group effects will be determined from the pairwise comparisons performed between Secukinumab regimens and placebo.

BASDAI at Week 12/16

The change from baseline to Week 12/16 in total BASDAI will be analyzed using a MMRM with treatment regimen and analysis visit as factors and weight and baseline score as continuous covariates. Treatment by analysis visit and baseline by analysis visit will be included as interaction terms in the model. An unstructured covariance structure will be assumed for this model. The significance of the Secukinumab treatment effect will be determined from the pairwise comparisons performed between Secukinumab regimens and placebo.

Other secondary variables

SF-36 PCS

For the change in SF-36 PCS, between-treatment differences will be evaluated using a mixed effect repeated measures model (MMRM). Treatment group and analysis visit will be included as categorical factors and baseline SF-36 PCS score and weight as continuous covariates. Treatment by analysis visit and baseline SF-36 PCS score by analysis visit will be included as interaction terms in the model. An unstructured covariance structure will be assumed for the model. The significance of the Secukinumab treatment effect will be determined from the pairwise comparisons performed between Secukinumab regimens and placebo.

Between-treatment comparisons for binary variables in the FAS population (e.g. ASAS20) at individual analysis visits will be evaluated using a logistic regression model with treatment as a factor and weight as a covariate for any analysis up to end of study.

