#### Treatment arms

Patients will be randomized 1:1:1 to one of the following treatment groups:

- **Secukinumab - delayed NSAID tapering:** Secukinumab 150 mg s.c. at weeks 0, 1, 2, 3, 4, 8, 12, 16 and 20 with placebo injections at Week 5, 6, 7 and 17, 18, 19 to maintain the blind.
- **Secukinumab – early NSAID tapering:** Placebo at weeks 0, 1, 2, 3 to maintain the blind; followed by Secukinumab 150 mg s.c. at Week 4, 5, 6, 7, 8, 12, 16 and 20 with intermittent Placebo injections at week 17, 18, 19 to maintain the blind.
- **Placebo:** Placebo at weeks 0, 1, 2, 3, 4, 5, 6, 7, 8 and 12. After the Week 16 assessments of the secondary endpoint have been performed, these patients will receive Secukinumab 150 mg s.c. at weeks 16, 17, 18, 19 and 20.

The patients will be stratified at randomization according to their status of prior TNF $\alpha$  inhibitor exposure, i.e. TNF $\alpha$  inhibitor naïve patients or TNF $\alpha$  inhibitor inadequate responders (TNF $\alpha$ -IR). The only condition that will be placed on enrollment targets for each stratum is that no less than 60% (i.e. 114) of patients are TNF $\alpha$  inhibitor naïve, i.e., no more than 40% (i.e. 76) of patients are TNF $\alpha$ -IR. In theory the percentage of TNF $\alpha$  inhibitor naïve patients could reach 100%, although that is not anticipated.

For primary analysis both the secukinumab treatment arms will be pooled and compared against placebo.

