## 2.2 Analysis sets

**Randomized set:** The randomized set will be defined as all subjects who were randomized.

**Full analysis set (FAS):** The FAS will be comprised of all subjects from the randomized set to whom study treatment has been assigned. Following the intent-to-treat principle, subjects will be evaluated according to the treatment assigned to at randomization, and in the actual stratum if stratified randomization is used.

**Safety set:** The safety set includes all subjects who took at least one dose of study treatment during the treatment period. Subjects will be evaluated according to treatment received.

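### The models for the confirmatory secondary hypotheses leave out the TNF-inhibitor randomisation stratum, which the primary model and the SAP's own model code include. The cost is about one power point per arm.

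*SAP*

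**What the plan says.** **Randomisation and primary model.** SAP 1.1 (Treatment arms) and Protocol 3.1 name a single stratification factor: "The patients will be stratified at randomization according to their status of prior TNF"-inhibitor exposure. SAP 2.5.2 and Protocol 9.4.2 fit the primary logistic model with treatment, TNF "status (previously exposed / never exposed), and CRP status (above central lab ULN / equal or below central lab ULN) as factors", and pool the two secukinumab arms by a linear contrast.

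**Secondary models.** SAP 2.7.2 says of ASAS20 at Week 12 (delayed arm) and at Week 16 (early arm) that response "will be evaluated using a logistic regression model with treatment as a factor and baseline weight as a covariate". The MMRMs for ASAS-NSAID and BASDAI use treatment, visit, weight, baseline score and interactions with visit. Protocol 9.5.1 gives the same covariates. Its general rule for binary variables is a "logistic regression model with treatment as a factor and weight as a covariate for any analysis up to end of study". None of these models has a TNF term.

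**SAP 5.4.** The ANCOVA text, the longitudinal text and the SAS code for the mixed and logistic models all include a stratification factor. The logistic text limits it to cases where it applies. STRATA is not defined there, but only one randomisation factor exists.

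**Precedence.** SAP section 1 says data are analysed according to Protocol Section 9, and SAP section 4 declares no change to protocol analyses. No sentence ranks 2.7.2 against 5.4.

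**The concern.** A factor used to balance the arms at randomisation normally belongs in the model. If it predicts outcome, leaving it out makes the test slightly conservative and costs power. Here the factor is already collected and already in the primary model.

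The tests affected are the weakest links in the hierarchy: H4 and H5 (each arm against placebo on ASAS20 at Week 12) must both be rejected before H6 can be tested. In addition, a programmer who follows 5.4 and one who follows 2.7.2 would fit different models to the same confirmatory endpoints.

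**Working it through.** **1. The plan's own figures.** For 56.9% versus 27.0%, two-sided 5%, 90% power:

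n = [1.960·√(2·0.4195·0.5805) + 1.282·√(0.569·0.431 + 0.27·0.73)]² / 0.299² = 55.1.

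The continuity correction, (n/4)·[1 + √(1 + 4/(n·0.299))]², gives 61.6, so 62 per group as stated. The continuity-corrected power for 127 versus 63 at 56.9% versus 35% is 77.5%, against the stated 78%.

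**2. Per-arm power without covariates.** For 63 versus 63 at 56.9% versus 35%:

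(0.219 − 1.960·0.0888) / 0.0866 = 0.519, so power is Φ(0.519) = 69.8%.

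**3. How strongly TNF status predicts ASAS20.** Stratum rates for the earlier phase 3 trial (MEASURE 2, Week 16) are in Protocol 1.1 and 3.6.
- Active 150 mg: (0.682/0.318)/(0.500/0.500) = odds ratio 2.14.
- Placebo: (0.311/0.689)/(0.241/0.759) = odds ratio 1.42.

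With 60% TNF-naive (the plan's minimum) and overall rates of 56.9% and 35%, these imply active rates of 64.4% naive and 45.7% inadequate responder (0.6·64.4 + 0.4·45.7 = 56.9), and placebo rates of 38.2% and 30.3% (0.6·38.2 + 0.4·30.3 = 35.0).

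**4. Simulation of the two models.** Settings: 190 patients, 1:1:1, permuted blocks within stratum, three-arm logistic Wald tests, 40,000 trials per row. Block size 6 and a weight covariate with no prognostic value are assumptions. Entries are power in %, treatment + weight → treatment + weight + TNF status.

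| Scenario | H4 | H5 | Both |
|---|---|---|---|
| 35% placebo, 60% naive | 69.86 → 70.86 | 69.96 → 70.97 | 55.57 → 56.82 |
| 35% placebo, 70% naive | 70.12 → 70.98 | 69.94 → 70.75 | 55.75 → 56.78 |
| 35% placebo, 80% naive | 70.29 → 71.09 | 70.22 → 70.92 | 55.94 → 56.82 |
| 35% placebo, 60% naive, odds ratio 2.14 in all arms (assumed) | 70.11 → 71.36 | 69.86 → 71.26 | 55.56 → 57.25 |
| 27% placebo, 60% naive | 93.56 → 93.90 | – | 88.82 → 89.38 |
| MEASURE 2 stratum rates, 60% naive | 96.58 → 96.78 | – | 93.85 → 94.20 |
| MEASURE 2 stratum rates, 70% naive | 97.43 → 97.60 | – | 95.43 → 95.68 |

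Both models are fitted to the same trials and disagree on H4 in about 1% of them, so the simulation error of a one-point gain is about √(0.011/40,000) = 0.05 points. A separate run of 20,000 trials for the first row gave 70.1 → 71.2 for H4 and 56.0 → 57.2 for both. A simpler run at the MEASURE 2 rates, with fixed stratum counts and no weight term (8,000 trials), gave gains of 0.4 to 0.6 points.

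**5. Type I error.** With no treatment effect and a 35% response, the weight model rejects H4 in 4.7 to 4.9% of trials and the weight + TNF model in 4.9 to 5.1%. Taking whichever model rejects still gives only 4.9 to 5.1%.

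**6. BASDAI.** With difference 1.8 and SD 2.8 (Protocol 9.7) and 63 per arm, the t-test has 94.7% power. If TNF status explains 1% to 5% of the variance (assumed), the SD becomes 2.8·√(1 − R²) and power is 94.9% to 95.7%, a gain of 0.2 to 0.9 points. Protocol 9.7 states about 91% for 62 per group. That difference does not bear on the size of the gain.

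**The case against.** The strongest reply is that nothing is broken. Protocol 9.5.1 and SAP 2.7.2 agree on the covariates, and each model, fixed in advance, is valid. SAP 5.4 reads as generic text: it speaks of several doses and several stratification factors, and it applies its longitudinal model to key secondary variables, a category that SAP 2.6 says does not apply. On that view 2.7.2 governs and adding TNF status is a preference.

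Most of this stands. 2.7.2 is the more natural reading, and no error-rate problem exists. What remains is that the gain is free and that the code printed in the SAP contradicts the text.

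Four stronger readings are tempting, and the documents do not support them.
- **The FAS definition requires adjustment.** Evaluating patients "and in the actual stratum if stratified randomization is used" (Protocol 9.1 has the same rule) says which stratum value a patient carries. It does not put that value in a model.
- **H5 has no model.** SAP 2.7.2 lists it ("H5: Secukinumab 150 mg s.c. (early tapering) is not different to placebo regimen"), and the general binary rule in Protocol 9.5.1 covers it. Only the Week 12 model paragraph fails to name the early arm.
- **H3 would be tested arm by arm.** The BASDAI paragraph mentions only pairwise comparisons, but H3 is stated as pooled ("H3: Secukinumab 150 mg s.c. (pooled Secukinumab groups) is not different to placebo regimen with respect to change from baseline in total BASDAI score") and so is its endpoint in SAP Table 1.2-1. The pooled estimator is simply not written out. A linear contrast and a two-level pooled factor reach the same verdict in 99.98% of simulated trials.
- **The power loss is large.** Assumed placebo rates of 55% and 20% by stratum, with a treatment odds ratio of 3, give a gain of 5.5 points (74.8% to 80.3%). The documents' placebo rates are 31.1% and 24.1%, so that case does not describe this trial.

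**Conclusion.** The point holds and is minor. The secondary models omit the only randomisation factor, the primary model includes it, and SAP 5.4 includes it in text and code without an explicit rule on which section governs.

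The cost is about 1 power point per arm for H4 and H5 at 35% placebo response (about 70% to 71%; both rejected, about 56% to 57%), and 0.1 to 0.3 points per arm at the MEASURE 2 stratum rates. These sizes rest on another trial's Week 16 subgroup rates, on an assumed block size and on weight not predicting response. The H5 and H3 wording gaps are editorial.

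**What to change.** Before unblinding:

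1. Add actual TNF status, coded as in SAP 2.5.2, as a factor to the logistic models for H4 to H6 and to the MMRMs for H2, H3 and H7 to H11. Keep weight. Record this in SAP section 4 as a change from Protocol 9.5.1.
2. State that STRATA in 5.4 is TNF status and that 2.5.2 and 2.7.2 govern. Make the 5.4 code match: CRP status and the pooled contrast for H1, and pooled contrasts for H2 and H3.
3. Editorial: name the early arm in the Week 12 ASAS20 paragraph, and write the pooled linear contrast for H3 in the BASDAI paragraph as the ASAS-NSAID paragraph does for H2.

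If the sponsor prefers the Protocol 9.5.1 models, removing the stratum from 5.4 for H2 to H11 also ends the conflict but forgoes the gain. CRP status in the secondary models is not requested, because it is not a randomisation factor.

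The cost is SAP wording, code and one entry in section 4. TNF status is already collected, so no further data, patients or visits are needed.
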